5. SUBJECT WITHDRAWALS

Participants will be withdrawn from the study if they become pregnant or incarcerated as described above. In addition, those who do not show up at the camp or misses 3 or more assessment points in a row will be withdrawn from the study. For peer leaders, if they do not complete the three training sessions, they will become disqualified. Those disqualified peer leaders, however, can continue their participation as regular teen subjects (campers) if they are 16-17 years, after re-consenting as a camper.

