2. CHARACTERISTICS OF STUDY POPULATION

2.1 Subject Characteristics

Asthma and its morbidity disproportionately affect minority children of low-income families in inner cities, where asthma severity has increased and poses serious challenges to achieving adequate asthma control.⁵ Disparate burdens of asthma and its adverse outcomes among minority children have been consistently documented in the past 20 years.^{4, 23-25} In 2010, asthma prevalence in black children under 18 years was twice that of white youths; children in families below the poverty threshold as defined by the US Census Bureau were 1.5 times more likely to report current asthma than those in families at or above 200% of the poverty line.² Compared with white youth, black inner-city children are 4 and 3 times more likely to have asthma-related ED visits and hospitalizations respectively.⁴ The three cities where the study will take place, Buffalo, NY; Baltimore MD; Memphis TN demonstrate high rates of pediatric asthma, high health care utilization and high morbidity and mortality rates, thus this study will take place in these cities that are most likely to benefit from a proposed intervention.

a) Number of Subjects:

A total of 378 adolescents (12-17 years) and 42 adolescent peer leaders (16-20 years) will be recruited for this study. The sample size (N=378) is based on the power analysis using a novel method developed by Roy et al.²⁶ for a 3-level hierarchical longitudinal design based on the program "RMASS." This method has the advantage of incorporating three levels from the sites and repeated-measures from each subject with random-effects of the time trends at both the subject- and site-level, which are assumed to be equivalent in terms of sampling proportions, number of groups and differential attrition rates over time. In this proposed study, quality of life, the primary outcome, was used to estimate the sample size. Using data from the previous study,²⁷ the longitudinal trajectories of quality of life and its treatment-by-time interactions based on subject-level randomization were modeled: the estimated treatment*time interaction coefficient was 0.6 units, estimated SDs for error was 15, and the random-slope was 1.76. These estimated values with a Type-I error rate (alpha) of .05 yielded a total sample size of 276 that would detect a

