time trend over eight time points (T1-T8) between groups with a power of .80. This sample size was estimated on the assumption that the analyses use multi-site hierarchical 3-level linear mixed-effects models. In the earlier study, the attrition rate of the inner-city subsample (n=55) was 27% including those who failed to attend the camp program (n=13, 23%) and those lost to follow-up (n=2, 4%). To compensate for a possible attrition rate of 27%, the total sample size was increased to 378 (126 for each site; 63 each of two groups).

b) Gender and Age of Subjects:

Recruitment will not be limited on gender. Based on epidemiological data, we will focus on adolescents from 12-17 years of age for campers and 16-20 years of age for peer leaders.

Participants will be stratified by gender and age (younger 12-14 years, older 15-17 years), which emerged as influential covariates in the PI's earlier study. Within each of four blocks generated by each combination of these two covariates, each subject will be randomly assigned to either group using a computer-generated randomization table. Stratified randomization will ensure a similar number of subjects representing each block in the two treatment groups, balancing the influence of age and gender. Stratified randomization will be done separately for each site, and centrally coordinated and managed. Within the treatment group, participants will be assigned to subgroups based on their age [younger (12-14 years) and older groups (15-17)] to allow the study team to adjust the levels of difficulty/complexity of program content delivered at the camp. In doing so, we will attempt to enhance participants' understanding of the information covered in the program. In the previous study, we found no differences in study outcomes or camp satisfaction between gender-matched groups and co-ed groups, so subgroups will be gender-mixed.

c) Racial and Ethnic Origin:

Enrollment of participants will not be restricted to any racial or ethnic groups. By recruiting participants from three cities with high prevalence and incidence of pediatric asthma, (again based on epidemiological data) we anticipate the sample demographic to have a higher proportion of minority populations representative of the neighborhoods targeted (Buffalo, Baltimore and Memphis.)

d) Vulnerable Subjects:

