4. METHODS AND STUDY PROCEDURES

4.1 Study Procedures and Assessments

Design: This study will use a two-group randomized controlled design implemented in three metropolitan cities: Buffalo, NY, Baltimore, MD, and Memphis, TN. The project coordinator and a research assistant in each city who are not involved in direct patient care of teens with asthma will be responsible for recruitment and consent process taking place in each site. Peer leaders will attend a three-day intense training session that will take place prior to camps, lead small-group instructional activities at a one-day camp (PLASMA group) and follow up their group members bimonthly for 15 months. Camp participants from each site (n=126) will be randomly assigned to the peer-led (PLASMA) group or the adult-led (control) group. Upon enrollment, participants will be stratified by gender and age (younger 12-14 years, older 15-17 years), and randomly assigned to either group within each of four blocks generated by the combination of gender and age strata. Each group will attend a separate day camp where an asthma self-management program will be implemented either by peer leaders (intervention) or healthcare professionals (control). After the camp, the intervention group will receive peer-leader contacts bimonthly for 14 months using phone calls or other communication technologies (e.g., emails, or short-message system (e.g., texting) of teens' choice. Adult instructors (healthcare professionals) will contact the control group bimonthly for 14 months using similar methods, but different contact topics.

Both groups (intervention and control – more details below) will provide data at enrollment (T1), 3 months later (T2), immediately following the camp (T3), and at 3-, 6-, 9-, 12-, and 15-months post-camp (T4-T8).

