10. DATA ANALYSIS AND DATA MONITORING

10.1 Planned Statistical Analysis: Analyses will be performed using SAS, and R⁵⁶ will be used as analysis software to ensure the validity and reproducibility of the results. We will perform descriptive statistics on each outcome measure to look for abnormality and outliers. If a measure is not normally distributed, transformation will be applied. We will identify and investigate outliers for sources of errors, and conduct preliminary analyses on data distribution and bivariate correlations to determine the appropriate statistical model as well as the final interpretation of the results. We will investigate missing data with pattern analysis for data missing completely at random (MCAR), missing at random (MAR) or missing not at random (MNAR), and use statistical methods appropriate for each type such as maximum likelihood and multiple imputation to impute missing values so full analysis can be performed with sensitivity. We will compute Cronbach's alphas for psychometric measures, and assess construct validity using exploratory or confirmatory factor analysis when appropriate. The PLASMA and control groups will be compared on baseline data to determine any systematic differences; if any are found, analyses will include the variables as covariates in the model to adjust for the imbalances.

Aim 1: A multi-site hierarchical three-level linear mixed-effects model,^{26, 56, 57} where level 1 represents repeated measures, level 2 = subject, and level 3 = site, will be used to analyze treatment differences and treatment-by-time interaction described in the following notation by Hedeker and Gibbons.⁵⁷

Aim 2: The mediating effects will be examined mainly using the mediation methods of Baron & Kenny.⁵⁸ When found significant, a multiple mediation analysis⁵⁹ procedure will be used to further determine whether the effect of PLASMA on quality of life is mediated jointly by multiple exploratory outcomes.

Aim 3: Moderating effects will be examined by multiple linear models and generalized linear models described in Berridge and Crouchley⁵⁶ or Chen and Peace⁶⁰ along with the above multi-site hierarchical three-level linear mixed-effects models.

Aim 4: This aim will be tested by applying the multi-site hierarchical two-level linear mixed-effects models described in the analysis for Aim 1, with level 1 representing longitudinal measurements and level 2 sites.

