Aim 5: The costs of services received during visits to a physician's office, outpatient department, or ED will be estimated by taking the global relative value unit for each service CPT (Current Procedural Terminology) code multiplied by a standard conversion factor.⁶¹ Hospital charges will be converted to costs using department-specific cost-to-charge ratio.⁶² Medications and dosages prescribed will be captured; standard wholesale unit cost from the Pharmaceutical Red Book⁶³ will be used to estimate medication costs. To calculate lost productivity costs of a family with a sick teen, we will estimate total lost income related to each participant by multiplying total number of work hours missed by a parent's hourly wage. Program costs will be estimated from the actual time peer and adult leaders spent in carrying out the program multiplied by hourly earnings, costs of equipment/ supplies, and overhead costs; program time will not include staff time for research-related tasks. We will estimate the average program cost per participant by study group, and include this estimate as one component of direct healthcare costs. The

medical or general Consumer Price Index⁶⁴ will be used to inflation-adjust costs to current year prices.⁶⁴ For each teen at each time-point, we will calculate total direct costs, direct costs by major category (office visit, hospitalization), indirect lost-productivity costs, and total direct and indirect costs. For withdrawals from follow-up, we will impute missing utilization and cost data assuming a linear trend in use and cost given prior experiences, where we will estimate weighted least square regression on log-transformed cost and obtain smearing-retransformed predictions.⁶⁵ For PLASMA and control groups separately, we will calculate the cost difference between each time point and baseline for each teen, assuming (s)he received “standard care” before treatment. Cost differences for each group will be modeled against follow-up points and individual covariates to estimate the independent impacts of each program on costs relative to standard care.

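### Camp no-shows are withdrawn after randomisation, so about 87–89 of 378 teens would have no post-camp quality-of-life data, and the planned model would return roughly the attenders' effect rather than the effect in all randomised teens

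*Combined protocol and SAP*

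**What the plan says.** Section 4.1 (Design) places randomisation before the camp: "Upon enrollment, participants will be stratified by gender and age", with random assignment within strata. T1 and T2 precede the camp, T3 follows it immediately, and T4–T8 run from 3 to 15 months after it. Section 5 then provides that "those who do not show up at the camp or misses 3 or more assessment points in a row will be withdrawn from the study".

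Section 2.1 (Number of Subjects) treats non-attendance as attrition. In the earlier study's inner-city subsample of 55, 13 teens did not attend camp and 2 were lost to follow-up. "To compensate for a possible attrition rate of 27%, the total sample size was increased to 378".

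For missing data, Section 10.1 will examine whether values are missing completely at random, "missing at random (MAR) or missing not at random (MNAR), and use statistical methods appropriate for each type", giving as examples "maximum likelihood and multiple imputation to impute missing values so full analysis can be performed with sensitivity". It names no analysis set and no specific missing-not-at-random (MNAR) model, and it does not say how withdrawn no-shows enter the Aim 1 model. Aim 5 is more definite: "For withdrawals from follow-up, we will impute missing utilization and cost data assuming a linear trend". That rule covers utilisation and cost, not quality of life.

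**The concern.** The withdrawal rule is triggered by an event after randomisation, and it ends collection of the primary outcome before any post-camp value exists. In the earlier study this event made up 13 of the 15 losses, so it is an expected feature of the trial. The usual reply is that a mixed model fitted by maximum likelihood, or multiple imputation, will deal with it. But the no-shows' only data precede treatment, so these methods as usually applied must assume that no-shows would have followed the attenders' post-camp course, and the data cannot test that.

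Section 1 states the goal as effectiveness and generalizability, and Section 7.2 foresees adoption by providers or payers as standard care. My reading, which the documents do not state, is that such an adopter needs the effect among all teens offered the program, including those who stay away. As planned, the trial would collect nothing that shows how far the attenders' result extends to them.

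**Working it through.** **Plan's own figure.** 276 / (1 − 0.27) = 378.1, which reproduces the stated 378. The components also agree: 13/55 = 23.6% (printed 23%), 2/55 = 3.6%, 15/55 = 27.3%.

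**Expected no-shows.** 378 × 0.23 = 86.9 and 378 × 13/55 = 89.3, so 87–89. The exact (Clopper-Pearson) 95% interval for 13/55 is 13.2%–37.0%; multiplied by 378 this is 50–140 teens.

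**Effect in all randomised teens.** Set the attenders' treatment-by-time effect to 1 and let no-shows have g times that effect. The all-randomised effect is 1 − p(1 − g), where p is the no-show proportion.
- g = 0: 0.770 at p = 0.23 and 0.764 at p = 13/55; 0.87 to 0.63 across the interval for p.
- g = 0.5: 0.885 and 0.882.

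Both values of g are assumptions.

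**What the planned type of model would return.** Inputs from Section 2.1: "estimated SDs for error was 15, and the random-slope was 1.76". Let A be a teen's information matrix X′V⁻¹X for intercept and slope from all eight visits, and B the same from T1 and T2 only. The expected intercept and slope differences are

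[(1 − p)A + pB]⁻¹ [(1 − p)A(0, 1)′ + pB(0, g)′].

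Section 2.1 gives neither the time unit nor the random-intercept SD. I therefore ran time per visit and per month (visits 3 months apart), intercept SDs of 1–30, intercept-slope correlations of −0.3 to 0.3, and 1.76 read as an SD and as a variance. The site level was left out. Results for the slope difference with g = 0:

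| Data from no-shows | p = 13/55, per visit | p = 13/55, per month |
|---|---|---|
| T1 and T2 only | 0.994–1.013 | 0.974–0.999 |
| A random half give T1–T8 | 0.864–0.871 | 0.856–0.866 |
| All give T1–T8 | 0.764 | 0.764 |

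Across the interval for p, the first row runs from 0.95 to 1.02. Keeping pre-camp data in the model thus leaves the estimate at about the attenders' value, and follow-up of even half the no-shows moves it about halfway to the all-randomised value.

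**Payments at Section 4.4 rates.** T4–T7 at $30 plus T8 at $50: 4 × 30 + 50 = $170 per teen. Then 170 × 87 = $14,790 and 170 × 89 = $15,130. If T3 is also paid at the $50 camp rate, the figure is $220 per teen: 220 × 87 = $19,140 and 220 × 89 = $19,580.

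**The case against.** The strongest reply is that no document states an all-randomised estimand. Both arms receive a manual-based camp and bimonthly contacts, so Aim 1 compares peer with adult leadership, and a contrast among attenders is a legitimate answer to that question. This stands in part: if no-show is unrelated to arm, the attender contrast is valid for attenders. It does not settle the matter, because the stated goal is effectiveness and a written rule stops data collection that could inform it.

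Second, the plan discloses no-shows, inflates for them, and commits to missing-data methods with sensitivity. That is correct. A reader might infer that missing data are ignored or that the analysis is restricted to attenders; Section 10.1 supports neither. The gap is that nothing concrete is specified for these teens, and that the methods named do not by themselves recover the all-randomised effect.

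Third, with attendance known, one can scale the attender effect by the attendance rate. That is true, but it only restates the zero-gain assumption.

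Fourth, pre-camp data may not exist for every no-show. Some may miss T2, and Sections 7 (Confidentiality) and 8 destroy the data of anyone who asks to withdraw. This stands, and the remedy has to account for it.

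A reader might also infer that the comparison between arms is biased. Unequal no-show is possible, since the arms attend separate camps. But Section 3.2 says assignment is concealed, Section 4.1 holds the camps within 2 weeks of each other, and no arm-specific rate is given. Such bias can be neither shown nor sized.

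**Conclusion.** The point holds and should be fixed. About 87–89 of 378 randomised teens would be expected to have no post-camp primary outcome because of the Section 5 rule. The 50–140 range is sampling uncertainty in the earlier 13/55, carried to three new cities by assumption; it is not the spread expected at a fixed 23%. Teens withdrawn for three missed assessments come on top and cannot be counted from the documents.

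If no-shows gain nothing, the planned model returns about 0.97–1.01 of the attender effect, where the all-randomised effect is 0.76–0.77 of it; if they gain half, the all-randomised value is about 0.88. These ratios rest on the assumed gains, a linear time trend and the ranges given above for the unstated inputs.

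It would go too far to say that the sample size overlooks no-shows, since 276/0.73 covers them. I give no power figure for the all-randomised effect. One would rest on the stated 80% at 276 and on 0.6 being an effect in attenders, which Section 2.1 does not say. Power may be lower if no-shows gain little.

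**What to change.** 1. **Section 5.** State that camp non-attendance or missed assessments do not by themselves end data collection. These teens are still sent the online T3–T8 questionnaires, timed from their assigned arm's camp date, unless consent is withdrawn. The pregnancy and incarceration withdrawals are unchanged.
2. **Section 10.1.** State that the primary analysis includes all randomised teens in their assigned arm with all available data, and that the attenders-only analysis is supportive. Count and report by arm the no-shows and the teens whose data are destroyed on a withdrawal request.
3. **Section 10.1.** Add one MNAR sensitivity analysis for teens without post-camp data. Vary the assumed departure from the attenders' post-camp course separately in each arm, for example 100%, 50% and 0% of the post-camp change, so that differential no-show is tested too.

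**Cost.** Protocol, SAP and consent wording must change; the online questionnaires already exist (Section 7, Confidentiality). Payments are as worked out above, and the plan should say whether T3 is paid for no-shows. Tracing time and the cost of keeping teens who miss three assessments cannot be sized from the documents. Response will be incomplete, so the missing-data assumption shrinks without disappearing, and the estimated effect may be smaller. The plan should say so; enrolling more teens is not needed for this point.

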6. REPORTABLE EVENTS

Adverse events (AEs) are defined as physical and psychological discomfort (boredom, fatigue, stress) related to completing multiple questionnaires and participating in the day camp program, intense self-management training/program. AEs will also include physical injuries during recreational activities at the camp. Any breach of confidentiality would also be an adverse event. These events are believed to be possible but are not automatically expected. Procedures will be implemented in order to prevent and address AEs during the study

Mechanism for Reporting Adverse Effects. The project staff will also periodically inquire about adolescents' reactions or feelings throughout the study. The project staff will report any AEs observed in relation to study participation to the site-PI and PI immediately. Review of adverse events will include: (1) Adverse events in aggregate, by attribution (expected or unexpected) and relationship to study intervention, (2) Whether the study accrual pattern warrants continuation/action, and (3) potential protocol violations. The PI will also monitor study safety by

weekly reviews of randomly selected cases for research staff's adherence to study procedure and IRB compliance (e.g., informed consent). The PI will continuously evaluate risks associated with research procedure and maintain subject confidentiality through weekly team meetings and conference calls with the project staff in other sites. The center coordinator will assist the PI in reviewing, capturing and reporting any adverse events and unanticipated problems to the IRB and NINR using interactive computer modules in the Clinical Data Management System. The PI will assess any external factors or relevant information that may impact the safety of participants or ethics of the study.

The research staff will report AEs to the PI and the site-PI immediately for each event. The PI will report to and discuss any identified AE with the Safety Management Committee (SMC). Decisions related to continued participation status of the subject will be reached within 10 working days by SMC consensus. The PI and site-PI will report the incident to the University of Rochester RSRB and relevant site IRB within 7 working days of each event. AEs identified during the camps will be recorded and discussed with the SMC immediately after the camps and reported to the UR RSRB and site IRB within 1-2 working days. AEs will be captured via the electronic system available for all three sites; the PI and center project coordinator will monitor and review these events weekly.

7. RISK/BENEFIT ASSESSMENT

Risks to Subjects

Potential Risks: This study will present minimal potential risks to subjects. Data will be collected primarily using questionnaires and noninvasive physiological measures (peak flow meters and spirometer). However, a small number of subjects may be stressed by having to complete multiple questionnaires every 3 months and monitor peak flow values daily during study participation. Due to the intensive nature of peer leader training and the camp education program, subjects may experience either fatigue and/or boredom. In addition, peer leaders may experience emotional distress potentially associated with their dealings with camp participants' psychological and behavioral issues as well as any issues related to the illness during bimonthly contacts. Also, injuries may also occur during participation in camp recreational activities. The likelihood of risks associated with the camp program, however, is minimal given the sufficient number of trained adult volunteers and the study staff who will closely monitor the conditions and the safety of camp participants during the camp.

Psychological/Physical Distress: To avoid worsening of physical or emotional preconditions, we will exclude those who have serious health (other than asthma) and emotional preconditions (e.g., severe depression, anxiety disorders, schizophrenia) as indicated in the eligibility criteria. Adult nominators (clinicians, teachers, etc.) of peer leaders will be informed of this eligibility criterion. For regular participants, the coordinator will confirm these criteria with parents. Adolescents and parents will be assured that, if the adolescent's responses demonstrate a risk to themselves or others, the adolescent's primary care provider or the family will be notified immediately.

This study involves minimal risk to participants as the study procedures are noninvasive in nature and do not require any changes in existing treatment regimens. Should the research team identify any participant with serious asthma symptoms that have not received proper treatment, we will encourage the subject to seek medical attention immediately or refer the subject to his/her primary care provider if known. The research team will hold weekly multi-site standing meetings to review participants' responses to the intervention and discuss any challenges or issues encountered in working with the participants.

Peer leaders will be trained to identify and immediately report to the research team any unusual, alarming comments or concerning behavior that they noted during bimonthly contacts. The research team will provide peer leaders with examples of reportable comments and behaviors.

The study team will closely monitor peer leaders' emotional distress potentially associated with their dealings with camp participants' psychological and behavioral issues as well as issues associated with the illness during bimonthly contacts. Specifically, the peer leader trainer or the site study staff will provide each peer leader with ongoing and regularly scheduled supervision and support through brief informal interviews on the phone upon completion of each bimonthly contact period for early detection of peer leaders' emotional burden. Any detected signs of distress will be reported immediately to the PI and site PI. All research staff will have a protocol to follow in instances of concerns: informing the family and the primary care provider and providing immediate referrals if indicated. Any questionable conditions occurring during the study will be discussed in-depth during weekly project meetings for referral as well as a decision related to continuing study participation.

The camps in Buffalo will be protected by liability and accident medical insurance provided by the University of Rochester in case of physical injury during camp participation. Non-UR sites (Baltimore and Memphis) will have subcontract with the UR, so will be subject to their own institutional terms and policies pertaining to research-related injuries. For each site, consent forms will contain specific statements describing how injuries resulted from study participation will be managed by the institution. Adult volunteers (primarily nursing students) will closely monitor and assist camp participants. The ratio of the volunteers and campers will be maintained at 1:6 to facilitate close surveillance. Each camp will be attended by a state-certified health practitioner (MD or NP) who will evaluate or treat asthma symptoms or minor injuries at the camp site. Each camp site will be equipped with medical supplies necessary to manage most medical emergency situations. Moreover, we will identify and contact a healthcare center with an ED facility located near the camp site prior to the scheduled camp date in order to ensure that the facility is prepared to manage any serious urgent health issues (e.g., asthma attack or severe physical injury) that may occur at the camp.

Because the spirometry procedure requires forced expiration, some subjects may experience exacerbation of asthma symptoms. To address promptly this rare undesirable effect, participants will be instructed to bring their rescue medication (e.g., Albuterol) to the camp and the 15-month follow-up. Trained clinicians will be available for assistance if needed. Any subjects with known risk factors for spirometry-induced asthma exacerbation will be excluded from the procedure. These tests will be performed in a room that is equipped with a respiratory emergency treatment kit.

Completing study questionnaires may cause boredom and fatigue in adolescents, although the PI's earlier study indicated that teens ages 13-20 spent less than 20 minutes on average on this task. Subjects both peer leaders and campers may also experience boredom and tiredness as they participate in the lengthy peer leader training or the camp education program. If the subjects express or present signs of boredom or fatigue, they will be allowed to take a short break during the administering of questionnaires. The electronic data capture system (REDCap) will be programmed in a way that it will permit multiple logins before completing questionnaires. Adolescents may also become physically and mentally exhausted during the peer leader training sessions and camp program. The research team will monitor any signs of discomfort shown by participants during peer leader training and the camp activities (instructional or recreational), and will be available to intervene in situations causing discomfort to the campers or peer leaders. Adolescents will be informed in the assent form and verbally that they do not have to respond to questions they do not wish to answer and that they are not obligated to attend the full camp program if they feel tired. In addition, adolescents will be encouraged to express any study-related questions or concerns at the time of contact or afterwards.

Confidentiality: To ensure confidentiality, subjects will be assigned an identification number, and they will be informed that all information will be held in confidence. Hardcopy data will be kept in a locked file cabinet in each site's project office. Subject information connecting subject names with identification numbers will be locked in a separate file drawer in each site-PI's office. Any printed subject information will be kept in the three site-PIs' locked drawers and will be shredded immediately if not used. Subjects will be informed that their parents or guardians will not have access to their responses for any of the measures. Adolescents and parents will also be assured that forms will be destroyed safely upon completion of the study. Parents and adolescents will be informed that only the research team, University IRB members, grant sponsors and auditors from NIH will have access to their responses. All data from any parent or adolescent requesting withdrawal from the study will be destroyed at the time of the request. Only aggregated data without any personal identifiers will be reported in publications or presentations.

Adolescents and parents will be informed that questionnaires will be completed online. The procedures to address privacy and confidentiality associated with online completion of measures will be discussed with subjects and indicated in the consent/assent forms. Certain technical information automatically collected during the visit to that Web site, including the Internet domain and Internet address (IP address), the type of browser and operating system, and the date and time of access, will be stored in log files on the server and will not be made available to parties other than the system administrators at the URMC. This information will only be used for purposes related to troubleshooting system problems. Subjects will be assured that online data will be transmitted in a secure method to a server database in the study center at URMC. To access the online questionnaires, a unique login and password will be assigned and given to each subject at enrollment. Logging in will afford access to completing the questionnaire only. No person who has logged on with different logins and passwords will be able to view any other person's responses to the questionnaires. All answers will be sent directly to the study center (URMC) database each time data are submitted; data will not be transmitted by any other means and cannot be retrieved by another person except the researchers in Rochester. In order to increase security, subjects will be counseled not to share these passwords with others, even those enrolled in the study. Data files will be backed up regularly. Project files and databases associated with the study will only be available to research personnel through the authorization of the PIs. In addition, study reports (such as aggregated data in progress reports) generated by the research team will provide total anonymity because no names or identifying information will be part of such reports. Participants and staff will be apprised of their rights and responsibilities under the Privacy Act of 1974, including penalties for violations. All staff involved with the research project will receive training on their function, roles, and responsibilities to protect and maintain privacy and confidentiality of research participants, and will complete NIH-approved training in this area.

7.2 Benefits to Subjects.

Although it is not automatically assumed that participants will benefit from study participation, the PI's earlier pilot study indicates potential benefits for participants. We anticipate that peer leaders will benefit from participation in the intensive three-day sessions. Leading the PLASMA program may provide peer leaders with opportunities to increase their knowledge and skills for effective asthma management and to develop and exercise leadership skills. Similarly, regular adolescent participants will have an opportunity to learn asthma self-management and build social networks with peers with the same illness. The camp will also provide participants with opportunities for entertainment and social experiences with asthma peers. The control group will attend an adult-led camp and receive the same information from a healthcare professional. If proven effective in this multi-site study, the PLASMA program can be adopted by healthcare providers or third party payers (e.g., HMO or Medicaid) as a standard care program to address asthma morbidity and mortality among inner-city adolescents and to contain health care costs for this group. Moreover,

information gained through this study may benefit other adolescents with asthma who would receive a similar program in the future.

Risk/benefit ratio. Risks to participants are reasonable in relation to anticipated benefits, with potential benefits far outweighing the risks. Because issues related to confidentiality will be scrupulously explained and managed, the primary concern is use of time. Anticipated benefits, including the peak flow meter and the program manual to keep, asthma self-management training and study incentives, are believed to be adequate compensation for the adolescents' time. Moreover, peer leaders and participants may experience an altruistic benefit in participating in a study that may benefit other adolescents with asthma in the future.

Self-reported (standardized questionnaires) and physiological (PEFR and Spirometry) data collected longitudinally (21 months) will capture systematic and dynamic processes by which the program modifies adolescents' self-management behaviors and health outcomes. The long-term observation will also allow the investigators to examine the sustainability of the intervention. Inclusion of multiple cognitive factors (knowledge, attitude, self-efficacy, and outcome expectations) as mediators will allow us to demonstrate intricate interrelationships or mechanisms between the intervention and asthma outcomes including asthma control and quality of life in adolescents. This study will also systematically investigate the economic impact (e.g., healthcare utilization, prescription and indirect costs) of the intervention, which will offer invaluable data to policy makers who might consider adopting the intervention as a standard care for teens with asthma. Moreover, this multi-site study involving three cities representing the Northeastern, Eastern and Southern sections of the US will provide evidence of the generalizability of the intervention and its impacts, which could further accelerate the adoption and implementation of the program to address the serious health threats of asthma in inner-city adolescents and to contain economic costs to society.

